4.5.3 Vital Signs

4.5.3.1 Definitions and Derivations

Vital signs, if abnormal, will be classified by whether the abnormality is clinically significant or not, the classification indicated directly in the eCRF by the investigator. Furthermore, five categories, corresponding to the number of occasions that a clinically significant abnormality in vital signs was observed for a patient, will be defined:

- 0 Clinically Significant abnormalities
- ≥ 1 Clinically Significant abnormalities
- ≥ 2 Clinically Significant abnormalities
- ≥ 3 Clinically Significant abnormalities
- ≥ 4 Clinically Significant abnormalities

4.5.3.2 Presentations

Vital signs will be summarised descriptively and presented according to the rules described in Section 3.3. The presentation will include a summary of both the distribution of values

themselves, by visit, and the distribution of change from baseline, also by visit. A summary according to the criteria described in Section 4.5.3.1 will also be provided and will be presented for the study periods described in Section 4.6.

Additionally, the change in vital sign abnormality status from the one observed at baseline to the one observed in connection to the minimum, or maximum, vital sign value, will also be presented.

4.5.4 Electrocardiogram

ECG measurements are taken at the Screening and Randomization visits only, and will be summarised together with other Baseline Characteristics, according to the rules described in Section 3.3.

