**Table 4      Objectives and Endpoints**

Objectives	Endpoints
Safety	
To assess the safety and tolerability of treatment with SZC, as adjunct to ACEi/ARB therapy (lisinopril or valsartan a) ), as compared to placebo	
Safety and tolerability will be evaluated in terms of AEs/SAEs, vital signs, clinical laboratory variables, and ECGs
 
Assessments related to AEs cover:
 

• Occurrence/frequency

• Relationship to study intervention as assessed by investigator

• Intensity

• Seriousness

• Death

• AEs leading to discontinuation of study intervention

a In case of a local market valsartan shortage, irbesartan will be temporarily used instead.

b Both of the primary endpoints must be met in order for the study to be declared successful, ie, co-primary endpoints.

c [Levin et al 2020](#); see Section 8.1.2.

ACEi, angiotensin converting enzyme inhibitor; AE, adverse event; ARB, angiotensin II receptor blocker; CKD, chronic kidney disease; ECG, electrocardiogram; eGFR, estimated glomerular filtration rate; ESKD, end stage kidney disease; SAE, serious adverse event; S-K, Serum potassium; SZC, Sodium zirconium cyclosilicate; UACR, urine albumin-to-creatinine ratio.

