### **7.1 Discontinuation of Study Intervention**

#### **7.1.1 Permanent Discontinuation of Study Intervention**

It may be necessary for a participant to permanently discontinue (definitive discontinuation) any or all study intervention (SZC, placebo, lisinopril, and valsartan).

Note that permanent discontinuation from study intervention is NOT the same as withdrawal from the study. If, upon discontinuation of study intervention, the participant chooses to withdraw from the study entirely, procedures described in Section [7.2](#) should be followed.

Participants should be discontinued from study intervention in the following situations as detailed below:

- Situations applicable to all study interventions
  - Participant decision. The participant is at any time free to discontinue treatment, without prejudice to further treatment.
  - Initiation of dialysis or kidney transplantation occurring prior to randomisation.

- Severe non-compliance with the CSP.
- Pregnancy (See Section [8.3.7](#)).
- Additional situations applicable to SZC/placebo
  - An AE that, in the opinion of the investigator or the Sponsor, contraindicates further dosing with SZC/placebo.
  - Local laboratory S-K < 3.5 or > 6.5 mmol/L at any time during the initiation phase (applicable only for initiation phase).
  - Local laboratory S-K < 3.0 mmol/L at any time during the study; the participant should immediately receive appropriate medical intervention.
  - Absolute QTc > 550 ms, or an increase in QTc interval > 60 ms from baseline to > 500 ms is reached; the participant should immediately receive appropriate medical intervention. The QTcF algorithm is recommended. All participants meeting the QTc > 500 msec criterion on study intervention should immediately have potassium assessed, if not already done within 1 hour of performing the ECG.
  - Chronic use of potassium binders other than SZC.
- Additional situations applicable to lisinopril/valsartan
  - An AE that, in the opinion of the investigator or the Sponsor, contraindicates further dosing with lisinopril/valsartan, including, but not limited to, angioedema, jaundice, or marked elevations of hepatic enzymes.
  - Severe hyperkalaemia as per titration algorithm (see [Appendix C](#)).
  - Advanced CKD with low eGFR (eg, sustained eGFR < 20 mL/min/1.73m^2).

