### **8.2.3 Electrocardiograms**

A 12-lead ECG will be performed with a properly maintained and calibrated machine. The recording should be done after the participant has been lying down to rest for at least

5 minutes. For participants with pacemakers, ECG variables should be read manually. ECG may also be performed according to clinical judgment and should be performed in connection with hypokalaemia (S-K < 3.0 mmol/L) or hyperkalaemia (S-K > 6 mmol/L), or as indicated based on any symptoms or clinical events (eg, cardiac arrhythmia).

The following ECG parameters should be collected: PR interval, RR interval, QRS duration, QT and QTcF intervals, and heart rate. An overall evaluation of the ECG results should also be performed.

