#### **Vital Signs, Laboratory Evaluations, and ECG**

The distribution of the measurements over time will be illustrated by presenting the summary statistics (mean, SD, median, minimum, maximum) of the values obtained at the study visits, as well as change from baseline to each of the respective visits. The occurrence of extreme measurements, eg, measurements falling outside pre-defined criteria at any point during a study phase, or measurements judged to be abnormal by the investigator, will be summarised by means of frequencies and percentages.

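### SAP Section 4.5.4 says ECGs are taken at screening and randomisation only and plans no by-arm summary of ECGs obtained after randomisation, contrary to Protocol Sections 8.2.3 and 9.4.3

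*SAP*

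**What the plan says.** The SAP's whole ECG plan is in Section 4.5.4: "ECG measurements are taken at the Screening and Randomization visits only, and will be summarised together with other Baseline Characteristics", under the general descriptive rules of Section 3.3. SAP Section 4.5 nevertheless counts ECG among the safety domains, and SAP Section 2 declares no departure from the protocol's analyses.

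The protocol says more, in four places.

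- **Endpoint (Section 3, Table 4).** "Safety and tolerability will be evaluated in terms of AEs/SAEs, vital signs, clinical laboratory variables, and ECGs". The objective it serves begins "To assess the safety and tolerability of treatment with SZC, as adjunct to ACEi/ARB therapy" and is a comparison with placebo.
- **Collection (Section 8.2.3).** A 12-lead ECG "should be performed in connection with hypokalaemia (S-K < 3.0 mmol/L) or hyperkalaemia (S-K > 6 mmol/L", and also when symptoms or clinical events suggest it. Intervals including QTcF are to be collected, with an overall evaluation.
- **Stopping criterion (Section 7.1.1).** SZC/placebo is to be discontinued if QTc exceeds 550 ms, or if "an increase in QTc interval > 60 ms from baseline to > 500 ms is reached".
- **Analysis (Section 9.4.3, under the shared heading for vital signs, laboratory evaluations and ECG).** Distributions over time are shown by "presenting the summary statistics (mean, SD, median, minimum, maximum) of the values obtained at the study visits, as well as change from baseline" at each visit. Extreme values, such as "measurements falling outside pre-defined criteria at any point during a study phase, or measurements judged to be abnormal by the investigator", are summarised as frequencies and percentages.

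**The concern.** The SAP asserts that ECGs exist at two visits and nowhere else. The protocol expects further ECGs during treatment, triggered by the potassium disturbances this trial sets out to manage: hypokalaemia on SZC, and hyperkalaemia on placebo after SZC is withdrawn. A programmer following SAP Section 4.5.4 would produce a baseline table and stop.

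The report would then list ECG as part of a safety comparison of SZC with placebo while showing no interval measurement taken on randomised treatment. SAP Section 4.5.2.1 does tabulate potassium below 3.0 and above 6.0 mmol/L, which are the thresholds in Protocol Section 8.2.3. Readers would therefore see how often the triggers occurred but not what the resulting ECGs showed.

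**Working it through.** No formula applies. The check sets the sections side by side.

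1. **Do the two ECG visits named in the SAP fall after randomisation?** No. Screening precedes all dosing. The footnote on the randomisation visit in the protocol's schedule of activities (Section 1.3, Table 2) puts that visit's assessments before randomisation, except for drug accountability. The randomisation ECG does follow the open-label SZC run-in of about 3 months. It therefore precedes randomised treatment but not SZC.

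2. **Does the protocol expect ECGs after randomisation?** Yes. The triggers in Section 8.2.3 are not confined to any phase. Section 7.1.1 sets QTc limits for participants on study intervention, and these can be applied only if ECGs are taken on treatment. *Only* in SAP Section 4.5.4 therefore misdescribes the data.

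3. **Which ECG outputs does Protocol Section 9.4.3 plan, and which survive?**

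| Output in Protocol 9.4.3 | In SAP 4.5.4 |
|---|---|
| Values by visit | Two visits, both before randomised treatment |
| Change from baseline by visit | None |
| Extreme or abnormal values at any point in a phase | None |

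The third row is the clear omission. The second depends on a scheduled post-randomisation ECG, which cannot be confirmed because the safety-assessment rows of Table 2 are missing from the text available for this review.

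4. **Does another SAP section supply the missing output?** No.
   - Section 3.3.3 keeps unscheduled data in analyses of extreme values, but no such analysis is defined for ECG, so the rule has nothing to act on.
   - Section 4.1.5.1 lists height, weight and BMI as baseline characteristics and does not mention ECG.
   - Section 4.5.3 gives vital signs by-visit values, change from baseline and abnormality counts. ECG, under the same protocol heading, gets none of the last two.
   - The listings in Section 4.5.1.2 are non-exhaustive and concern adverse events. An ECG listing is possible but not specified.

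5. **Is the difference declared?** No. SAP Section 2 states that nothing was changed from the protocol.

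Result: the number of ECG outputs planned on post-randomisation data is 0 in either arm.

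**The case against.** The strongest reply is that the gap costs little, because a serious ECG finding has other ways into the report. That is largely right.

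- Protocol Section 7.1.1 calls for SZC/placebo to be discontinued when a QTc limit is met, and Section 7.1.1.1 has the time and reason recorded.
- If a limit is met and treatment continues, SAP Section 3.3.5 makes this an important protocol deviation, and Section 4.1.3.2 summarises those.
- Protocol Section 8.3.5 directs clinically relevant deteriorations to adverse event reporting. SAP Section 4.5.1.2 tabulates adverse events leading to discontinuation, interruption or dose reduction by arm.

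A reader might infer that QTc cases would be invisible unless an investigator filed an adverse event. The documents do not support that. What these routes do not give is the interval measurements, the number of participants with any post-randomisation ECG, or a count against the QTc limits by arm.

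A second reply is that triggered ECGs cannot answer the safety question well. Potassium and symptoms depend on treatment, so the chance of having an ECG may differ between arms. This stands, and it limits the remedy to description. It does not explain why the extreme-value summary in Protocol Section 9.4.3 is absent.

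A third is that Protocol Section 8.2.3 says an ECG should be performed, so not every potassium episode will yield one. This also stands.

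Finally, the SAP was cut back after premature termination. That could justify a shorter report, but the amendment history does not give it as a reason for the ECG plan, and Section 2 declares no change.

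**Conclusion.** The SAP and protocol conflict on when ECGs are obtained, and the SAP omits, undeclared, the planned summary of extreme or abnormal ECG values during the maintenance phase. Post-randomisation ECG outputs planned by arm: none. This is worth correcting because ECG is a named safety endpoint. It does not affect the co-primary or secondary efficacy analyses.

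The number of participants concerned cannot be stated. The documents give no rate for potassium below 3.0 or above 6 mmol/L, and the target of 1360 randomised is not a usable base for a trial that closed early.

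Three stronger readings are not supported:

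- That the SAP reports only ECGs free of SZC exposure. The randomisation ECG follows the open-label run-in.
- That an ECG analysis was removed without being logged. The amendment history records differences between SAP versions, and the earlier text is not available, so it cannot show whether Section 4.5.4 ever read differently.
- That a by-visit change-from-baseline analysis of ECG was certainly lost. No scheduled post-randomisation ECG can be shown.

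The conclusion assumes that at least some triggered ECGs were done and recorded, as Protocol Section 8.2.3 intends.

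**What to change.** Rewrite SAP Section 4.5.4 as follows.

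1. Keep the baseline summary, and limit *only* to scheduled ECGs.
2. For the maintenance phase, add one table by arm with all SAS-MP participants as denominator. It should give the number with any post-randomisation ECG, the number meeting the protocol's own QTc limits (above 550 ms, or a rise of more than 60 ms to above 500 ms), and the number judged abnormal by the investigator. State which baseline the rise is measured from, since SAP Section 3.3.1.1 defines one for each phase.
3. Add a listing of these ECGs with the concurrent potassium value.
4. Label both outputs descriptive: triggered ECGs are a selected sample, and ascertainment may differ by arm.

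If the sponsor prefers to omit these outputs because of early termination, SAP Section 2 should say so and name the ECG summary in Protocol Section 9.4.3 as not performed.

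The cost is a few lines of SAP text, one short table and one listing. Protocol Section 8.2.3 asks for the parameters to be collected, but the documents do not show how unscheduled ECGs enter the database, so confirm that first.

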4.6 Immunogenicity

Not applicable.

5 INTERIM ANALYSIS

Not applicable.

7 APPENDIX

7.1 The mapping of CKD aetiology class

For the purpose of convenience, some of the categories of the CKD aetiology as collected in the eCRF will be combined for the sub-group analyses. It will be done as follows:

| Etiology in eCRF | Sub-group analysis class |
|-------------------------------------|------------------------------------|
| Cystic kidney disease | Cystic kidney disease |
| Diabetic nephropathy | Diabetic nephropathy |
| Ischaemic/Hypertensive nephropathy | Ischaemic/Hypertensive nephropathy |
| Chronic glomerulonephritis | Chronic glomerulonephritis |
| Renal artery stenosis | Other |
| Chronic pyelonephritis (infectious) | Other |
| Chronic interstitial nephritis | Other |
| Obstructive nephropathy | Other |
| Unknown | Other |
| Other | Other |

7.2 The assignment of countries to regions

The division of countries into regions, for the purpose of, e.g., sub-group analyses, will be performed as follows:

| Country | Region |
|-------------|---------------|
| Argentina | South America |
| Brazil | South America |
| Bulgaria | Europe |
| Canada | North America |
| China | Asia |
| India | Asia |
| Italy | Europe |
| Japan | Asia |
| Malaysia | Asia |
| Mexico | North America |
| Poland | Europe |
| Philippines | Asia |
| Russia | Europe |
| Spain | Europe |
| Taiwan | Asia |
| Thailand | Asia |
| Turkey | Asia |
| Ukraine | Europe |
| USA | North America |
| Vietnam | Asia |

7.3 Sample size determination and the different causes for missing data during the randomized treatment phase

Approximately 3000 participants will be enrolled (screened) to achieve approximately 1500 participants receiving at least one dose of SZC during the initiation phase, consequently leading to a target of 1360 participants randomly assigned to SZC or placebo.

Note that “enrolled” refers to a participant’s, or their legally acceptable representative’s, agreement to participate in the study following completion of the informed consent process.

The assumptions for variability of the eGFR measurements between and within participants used in the calculation below are taken from the DECLARE study (D1693C00001 [NCT01730534]): between-participant SD (i.e., SD of the random slopes) of 2.6 and within-participant SD (i.e., SD of the residuals) of 7.7. The difference in slopes in the 2 treatment arms is assumed to be 0.75, a magnitude that is deemed clinically relevant. It is also assumed that no acute effects are present, i.e., that the decline in eGFR over time in both treatment arms is well-approximated by a single line with a particular slope.

Given this, and assuming a two-sided test of a difference in slopes based on a linear mixed model, with a two-sided significance level of 0.05, is performed, then approximately 1220 participants with complete eGFR data will provide a power of 91% for the evaluation of total slope. This is true provided the following time points for eGFR assessment, in terms of weeks since randomisation, are observed for each participant as a minimum: 0 (randomisation), 6, 12, 16, 20, 24, 46, 69, 92, 96, 100, and 104.

Under the same assumptions (i.e., a difference in slopes of 0.75, no acute effect), the power for the chronic slope will be approximately 85%. The evaluation of the chronic slope is assumed to start at 12 weeks.

It is expected that approximately 20% of the eGFR data will be missing. As the eGFR data is correlated within participant, it is assumed that the data points available for a participant will provide information on the missed evaluations, and 20% of missed data would roughly correspond to approximately 10% of randomised participants with no eGFR data available. Hence, 1360 participants will be randomised in the maintenance phase.

Possible Causes for Missing Data during the Randomised Treatment Phase

The initial expectation that approximately 20% of eGFR measurements during the randomised treatment phase will be missing, is largely inferred from DAPA-CKD ([Heerspink et al 2020](#)). Death from any cause and ESKD were identified as the 2 potential main contributors for missing eGFR data. Looking at the placebo group in the aforementioned publication, it is expected that approximately 7% of participants will reach ESKD during the 2 years of randomised treatment phase, and approximately 6% of participants will die. It should be noted that the DAPA-CKD study had a somewhat healthier patient population that included patients with eGFR between 25 and 75 mmol/L (10% of the patient population in the study had an eGFR > 60 mmol/L). In addition, the hyperkalaemia requirement in the STABILIZE-CKD study might lead to a lower baseline eGFR in general, so a somewhat larger percentage of missing data due to the reasons mentioned above is expected. Tentatively, the expectation is that approximately 15% of the missing values will originate from ESKD or death.

In addition to these 2 major reasons, it is expected that data points will also be missing due to a number of smaller issues, such as participants not attending visits, blood samples not being analysable, and participants discontinuing the study, or discontinuing treatment and choosing an alternative follow-up option that precludes blood sampling. The magnitude of such smaller issues is difficult to predict, but it is tentatively expected that they might, cumulatively, lead to an additional 5% of the data points being missing, which would, together with ESKD and death, add up to approximately 20% of missing data.

Signature Page for VV-RIM-06297330 v1.0

Approve: Document Level Task
Verdict: Approved

PPD

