#### 4.2.2 Rationale for the Endpoints

##### 4.2.2.1 Rationale for the Primary Endpoints

The co-primary endpoints (ie, eGFR at and after randomisation and eGFR at and after 12-week visit) are appropriate for the objective of the study. These endpoints should reflect the combined results of the proposed SZC renoprotective mechanisms that include enabling the use of optimal ACEi/ARB therapy, and the anticipated effects on S-K, bicarbonate, and aldosterone levels as described in Section 2.2.3.

Data from observational cohorts as well as from randomised clinical studies support the validity of eGFR slope as a surrogate measure for kidney function decline (Astor et al 2011, Coresh et al 2014, Gansevoort et al 2011, Matsushita et al 2015, Turin et al 2013, Van der Velde et al 2011).

Furthermore, large observational and clinical studies have shown that an improvement in total eGFR slope predicts/translates into benefit on clinical kidney outcomes, for instance:

- In a patient-level meta-analysis of observational data from 122664 CKD participants with eGFR < 60 mL/min/1.73m^2, a reduction in eGFR slope decline by 0.75 mL/min/1.73m^2/year over 2 years was associated with a 30% lower risk of subsequent ESKD ([Grams et al 2019](#)).
- In a patient-level Bayesian meta-analysis including 47 clinical studies and 60620 participants (2018 NKF/FDA/EMA Workshop), a treatment effect of 0.75 mL/min/1.73m^2/year in the total eGFR slope predicts an average 27% lower hazard for the treatment benefit on the clinical endpoint ([Inker et al 2019](#), [Levey et al 2020](#)).

It is the Sponsor's view that eGFR slope is a clinically relevant surrogate for CKD progression and use of eGFR slope allows faster and more efficient clinical trials in CKD. Due to the observed acute haemodynamic effects of RAASi and SZC on eGFR measures, both total eGFR slope and chronic eGFR slope are used in this study to mitigate the potential impact on kidney function assessment and minimise the risk of a type 1 error. Accordingly, this is expected to show a clinically relevant difference favouring SZC and will reflect a true effect on irreversible loss of kidney function.

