3.3.4 Multiplicity / Multiple Comparisons

Statistical testing will be performed for all primary and secondary hypotheses. In all cases, the null hypothesis will be that of no difference between the treatment arms (SZC vs placebo), with the two-sided alternative of there being a difference. Two primary hypotheses (corresponding to the evaluation of the difference in total and chronic eGFR slope, respectively) are defined in the study.

The family-wise Type I error rate will be controlled in the strong sense over the families of primary and the secondary hypotheses i.e., regardless of whether the hypotheses covered are true or false.

Two co-primary hypotheses (corresponding to the evaluation of the difference in total and chronic eGFR slope, respectively) are defined in the study. The two hypotheses will be tested in parallel (i.e., with no pre-defined order) using the whole significance level alpha.

Provided both primary hypotheses are rejected, the testing will proceed to the secondary hypotheses. A fixed sequence MTP will be applied to the family of all secondary hypotheses, with the order in the sequence following the order specified in Table 2.

In accordance with the fixed sequence MTP, significance for a hypothesis will be declared if the corresponding two-sided p-value is smaller than 0.05, provided that all other preceding hypotheses in the sequence have been rejected.

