4.2.1.1 Main analyses

To evaluate the primary objective a linear mixed effects model will be fitted for each of the primary endpoints. It will be based on the eGFR values obtained at the scheduled visits at and after randomisation (total slope) and at and after 12-week visit (chronic slope) respectively as the dependent variable. The following covariates will be included as fixed effects in the model, in addition to the ones specified [above](#):

- Time (continuous) since randomisation (days)
- Time and treatment interaction
- UACR at randomization

If the model as specified above becomes ill-conditioned or encounters issues with convergence due to too few observations in one of the categories, the corresponding fixed effect will be removed from the model.

In addition, two random effects, intercept and slope corresponding to the time since randomisation, will be incorporated, with an underlying assumption of an unstructured covariance matrix between the two. A covariance matrix that assumes independence between the residuals within each participant but allows for a different standard deviation at each visit, will be applied. Because of that dependence on visit, and due to the early close-down of the study and the ensuing unavailability of late eGFR measurements, only measurements taken up to and including visit 17 (week 69) will be included in the mixed-effects model; however, all available data, including the (quite few) late eGFR measurements beyond visit 17 (week 69), will be summarised descriptively and listed.

The null hypothesis of no difference in slope between SZC and placebo will be tested by considering the fixed effect of time and treatment interaction term in the model. The estimates of the mean slopes obtained from the model, as well as the estimate of the difference between the two slopes, together with two-sided 95% confidence intervals, will be presented. For the difference in slope, the corresponding p-value will also be provided.

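### SAP 7.3 carries forward 91% and 85% power from the 104-week design without saying so, while the SAP's main analysis stops at week 69, where 1220 complete participants would give about 53% and 39%

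*SAP*

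**What the plan says.** SAP 7.3, which repeats Protocol 9.2, states that "approximately 1220 participants with complete eGFR data will provide a power of 91% for the evaluation of total slope". The next sentence makes this conditional on twelve eGFR time points per participant, the last four at weeks 92, 96, 100 and 104. Under the same assumptions, "the power for the chronic slope will be approximately 85" per cent. The section reads in the present and future tense and does not say that it describes a superseded design.

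SAP 4.2.1.1 says of the main model that "only measurements taken up to and including visit 17 (week 69) will be included in the mixed-effects model", and gives the early close-down as the reason. Table 2 writes the same limit into the definition of both co-primary endpoints. The primary analysis in Protocol 9.4.2.1 has no such cut. SAP Section 2 nevertheless reports that nothing changed from the protocol's analyses.

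Success needs both slopes. SAP 3.3.4 has it that "Provided both primary hypotheses are rejected, the testing will proceed to the secondary hypotheses", and the footnote to Protocol Table 4 makes the two endpoints co-primary. SAP 7.3 gives power for each slope separately and none for the pair.

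**The concern.** A slope is estimated mainly from how widely the measurements spread in time. Dropping everything after week 69 removes the four late visits that carry most of that spread, so the power calculated for 104 weeks cannot carry over to the week-69 model, whatever the number of participants. Yet the SAP states only the 104-week figures.

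What is at stake is how a null result would be read. The SAP calls 0.75 clinically relevant. Set against 91% and 85% power, a non-significant result would look like good evidence that a difference of that size is absent. The analysis actually specified has much less ability to show it, and the SAP does not say how much less.

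**Working it through.** **Inputs.** SAP 7.3 supplies the variability: "between-participant SD (i.e., SD of the random slopes) of 2.6 and within-participant SD (i.e., SD of the residuals) of 7.7". It also supplies a slope difference of 0.75, no acute effect, a test "with a two-sided significance level of 0.05, is performed", a chronic slope from week 12, and N = 1220 complete. The unit is per year, because Protocol 4.2.2.1 gives "a treatment effect of 0.75" per year as the relevant total-slope effect. Allocation is 1:1 (Protocol 4.1.4).

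**Time points (weeks).**
- Original plan, as listed in SAP 7.3: 0, 6, 12, 16, 20, 24, 46, 69, 92, 96, 100, 104.
- Week-69 cut, every scheduled central-laboratory eGFR visit: 0, 6, 12, 16, 20, 24, 34, 46, 57, 69. This comes from Protocol Table 2. The table text is broken, but the eGFR row reads as marked at every visit from week 6.
- Week-69 cut, only the points listed in 7.3: 0, 6, 12, 16, 20, 24, 46, 69.

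**Formulas** (t in years = weeks × 7/365.25).
- Sxx = Σ(t − mean t)².
- V = 2.6² + 7.7²/Sxx = 6.76 + 59.29/Sxx.
- SE of the slope difference = √(4V/N).
- Power = Φ(0.75/SE − 1.96).
- Joint power is a bivariate normal probability. In this model the covariance of the two slope estimates equals the variance of the total-slope estimate, so their correlation is SE(total)/SE(chronic).

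**The plan's own figures first, N = 1220.**
- Total: Sxx 6.71, V = 6.76 + 59.29/6.71 = 15.60, SE = √(4 × 15.60/1220) = 0.226, power Φ(3.32 − 1.96) = 91.3%.
- Chronic: Sxx 4.86, V = 18.97, SE 0.249, power Φ(3.01 − 1.96) = 85.3%.
- Correlation 0.226/0.249 = 0.91; both slopes 84.1%.

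Both stated figures reproduce, which supports using the same model for the cut.

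**Week 69, every scheduled visit, N = 1220.**
- Total: Sxx 1.70, V = 6.76 + 59.29/1.70 = 41.64, SE 0.369, power Φ(2.03 − 1.96) = 52.8%.
- Chronic: Sxx 1.10, V = 60.61, SE 0.446, power Φ(1.68 − 1.96) = 39.1%.
- Correlation 0.83; both slopes 35.0%.
- Difference detectable with 80% power, (1.96 + 0.84) × SE: 1.04 total and 1.25 chronic.

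| Analysis | N, all complete | Total | Chronic | Both |
|---|---|---|---|---|
| Week 104, points listed in 7.3 | 1220 | 91% | 85% | 84% |
| Week 69, every scheduled visit | 1220 | 53% | 39% | 35% |
| Week 69, points listed in 7.3 | 1220 | 45% | 33% | 29% |
| Week 69, every scheduled visit | 1360 | 57% | 43% | 39% |
| Week 69, every scheduled visit | 1000 (assumed) | 45% | 33% | 29% |
| Week 69, every scheduled visit | 500 (assumed) | 25% | 19% | 15% |

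The last two rows only show a range, because the documents do not give the number randomised when the study stopped.

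**What a null could still show.** With N = 1220 and every scheduled visit, the 95% interval has half-width 1.96 × 0.369 = 0.72 for total slope and 1.96 × 0.446 = 0.87 for chronic. An interval would exclude 0.75 from above only if the estimate fell below 0.75 − 0.72 = 0.03 (total) or 0.75 − 0.87 = −0.12 (chronic).

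**The case against.** The strongest reply is that 7.3 is true as written. It is conditional on the week-104 schedule, it never claims this power for the week-69 model, and the amendment history says it was added from the protocol for convenience. The early stop and the week-69 limit appear throughout SAP 4.2, so a careful reader would not take this for a fully followed trial. SAP 4.2.1.1 already asks for 95% confidence intervals, which will show the precision achieved. Power restated after termination changes neither the sample size nor the test.

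Much of this stands. A reader might infer that 91% and 85% are miscalculated; they are not. A reader might also treat 53%, 39% and 35% as a ceiling. They are not one, since 1360 complete participants would give 57%, 43% and 39%. Nor are they the power of the analysis that will be run, which depends on an N and a follow-up that the documents do not give. Joint power also adds little under the original design: 84% against 85% for the weaker slope.

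What does not stand is that the reader has been told enough. The note on origin is in the amendment history, not in 7.3. Section 2 says nothing changed. The SAP reports the early stop but nowhere its consequence for power. The calculation asked for uses the planned 0.75, not the observed effect, so the usual case against post-hoc power does not apply.

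**Conclusion.** The point holds as an inconsistency within the SAP. Its power statement depends on measurements at weeks 92 to 104 that its own main analysis excludes, and it carries no label saying so. On the SAP's own SDs and difference, the cut takes power for both slopes from 84% to about 35% with 1220 complete and every scheduled visit used, or about 29% on the listed time points alone. In no case examined does either slope come near its stated power.

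The figures assume no acute effect, complete follow-up to week 69 and a constant residual SD. SAP 4.2.1.1 allows visit-specific residual SDs and adds covariates; no values are given, so these are not modelled. Fewer participants or incomplete follow-up would lower power further.

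A reader might go on to infer that any non-significant result must be called inconclusive. The documents do not support that. A non-significant interval lying wholly below 0.75 would speak against the planned difference, though at this precision the estimate would have to be close to zero or negative. Whether the week-69 cut should have been made is a separate question.

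**What to change.** In SAP 7.3:
- Label 91% and 85% as the original 104-week plan and say that they do not apply to the week-69 analysis.
- Add the power for each slope and for both jointly, and the detectable difference, for the week-69 analysis at the actual N and follow-up.
- State that a non-significant result will be interpreted by whether the 95% confidence interval excludes 0.75, not by the original power.

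In SAP Section 2, replace the statement that nothing changed with an account of the week-69 limit. The amendment history already marks that change as not in line with the protocol.

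The cost is a few lines of text and one short calculation. No model, test or dataset changes. The stated power becomes less favourable.
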